### 2.3 Methods

Patients will be assessed and treated by the *Centro di Trattamento Integrato - Disturbi Alimentari e Obesità* (*CTI-Disturbi Alimentari e Obesità*). Two therapists will be involved in the trial: one CBT-trained, the other trained in both CBT-F and MIT. Both therapists will be supervised throughout the trial. The CBT-E arm will be supervised by a certified Associazione Disturbi Alimentari (ADA) supervisor, the MIT/CBT-F arm will be supervised by one of the developers of MIT, also a trainer of the Società Italiana di Terapia Comportamentale e Cognitiva (SITCC). A research assistant will manage the psychometric test administration and will liaise regularly with the clinical team.

#### 2.4 Participants

Twenty consecutive participants will be recruited at the CTI Disturbi Alimentari e Obesità. All participants will be aged 18 years or over and treatment-naive. They will be screened for a main diagnosis of ED in the past 6 months. Inclusion and exclusion criteria are reported in Table 1.

Inclusion Criteria	Exclusion Criteria
Aged >18 years	Acute psychotic episode, psychotic symptoms, Bipolar I disorder; antisocial personality disorder
ED diagnosed in the past 6 months	Suicidal ideation
Seeking treatment for eating disorder	Substance abuse
Able to provide written, informed consent	Previous psychological intervention for other eating disorders
BMI > 18.5	Currently involved in other ongoing treatment

Table1 Inclusion and Exclusion Criteria

All participants meeting inclusion criteria will be informed about the trial and will decide whether to take part. A regular ED-focused treatment will be offered to all participants excluded from the trial or who decline participating. All participants will give written informed consent before participation.

Drop-out rates from each arm will be reported for patients withdrawing during treatment and those lost to follow-up. Treatment is delivered in a private center therefore participants are paying for their care, however there is no financial incentive to participate in the trial. The study protocol is written in accordance with the European Union Standards of good clinical practice and in accordance with the Declaration of Helsinki. The protocol has been approved by the Ethics Committee of the Department of Dynamic and Clinical Psychology of "La Sapienza" University (Rome) Prot. n. 0000781, 05/13/2022 - [UOR: SI000092 - Classif. VII/15]

### 2.5 Measures

Primary, secondary and exploratory outcomes of the present study will be assessed over time using the following psychometric measures:

- Eating Disorder Examination Questionnaire (EDE-Q6, Fairburn & Beglin, 1994): A self report measure assessing eating disorders over the past 4 weeks, providing a measure of the range of severity of eating disorder features.
- Eating Attitude Test (EAT-26, Garner & Garfinkel, 1979): a self-report measure for identifying the presence of "eating disorder risk" based on attitudes, feelings and behaviors related to eating. It assesses general eating behaviour and risky behaviours.
- Clinical Impairment Assessment Questionnaire (CIA 3.0): a self-report measure f assessing the severity of psychosocial impairment due to eating disorder features over the past 28 days (Bohn and Fairburn, 2008).
- Binge Eating Scale (BES, Gormally et al., 1992): a self-report questionnaire of the behavioral, cognitive and emotional features of objective binge eating (OBE).
- State-Trait Anxiety Inventory (STAI): a self-report measure of trait and state anxiety (Spielberger, Gorsuch, Lushene, Vagg, & Jacobs, 1983).
- Beck Depression Inventory (BDI): a self-report measures of depression (Beck, et al., 1961).
- Symptom Check List (SCL-90): a measure of psychopathology symptoms and their intensity at a specific point in time.
- Difficulties in Emotion Regulation Scale (DERS; Gratz & Roemer, 2004): a self-report scale measuring individual differences in the ability to identify, accept and manage emotional experiences. This measure help in understanding emotional dysregulation that might underlie the disorders.
- Structured Clinical Interview for DSM-5 Disorders (SCID-5; Michael B. First, Janet B.W. Williams) for assessing and defining DSM-5 Model for Personality Disorders.
- Toronto Alexithymia Scale (TAS 20; Taylor & Bagby, 1992) that assess difficulties in understanding, processing, or describing emotions.
- Working Alliance Inventory-Short Revised (WAI,-SR Hatcher & Gillaspy, 2006) that measure the therapeutic alliance by assessessing three main aspects of the therapeutic alliance: agreement on the tasks of therapy, agreement on the goals of therapy and development of an affective bond.

[figure not shown]
All the psychometric tests will be administered at baseline, after 10 sessions (with the exclusion of SCID-5 Interview which will be only administered...), at the end of the treatment and in the following 3, 6, 12, 18 and 24 months after the treatment. The WAI will be administered monthly. All measures will be carried out by the research assistant who will be trained and weekly supervised.

## 2.6 Randomization/treatment allocation

Each participant will be randomized in one of the two experimental conditions by allocation concealment. In particular, randomized-permuted blocks will be used. The research team will be also blind to the randomized allocation. Group allocation will remain concealed until the end of the assessment stage.

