CBT-E treatment will consist of four stages. In the first Stage, the treatment will be focused on achieving a shared understanding of the patient's eating disorder and the related maintenance factors. In this phase the patient will be helped to regulate and stabilize his eating habits and so to address his weight concerns. In the second stage, progress made is reviewed in detail. In the third stage, the sessions will be focused on the central processes that are maintaining the psychopathology of the patient's eating disorder. In particular, this involves in addressing concerns about weight and body shape, cognitive and caloric dietary restriction, events and emotions that affect nutrition. in phase three and four clinical perfection, low global self-esteem, intolerance of emotions and interpersonal difficulties are also addressed.

Towards the end of the third stage and during the fourth stage, procedures will be also implemented to minimize the risk of short- and long-term relapse.

Each experimental condition will include up to 10 participants. In both conditions participants will receive an assessment session by a researcher who is blind and independent. In both arms, review session will be scheduled 2 weeks after the end of therapy to evaluate progress and to address any remaining or emerging issues.

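### Blinded assessment is claimed but not protected: one assistant collects every measure and is in regular contact with a clinical team that has, in effect, one therapist per arm

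*Combined protocol and SAP*

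**What the plan says.** Two places claim blinding. Section 2.6 says "The research team will be also blind to the randomized allocation" and then "Group allocation will remain concealed until the end of the assessment stage". The account of standard treatment in 2.7.2 says "In both conditions participants will receive an assessment session by a researcher who is blind and independent".

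Two other places describe who does the work. Section 2.5 says "All measures will be carried out by the research assistant who will be trained and weekly supervised", and for the alliance measure "The WAI will be administered monthly". Section 2.3 says "A research assistant will manage the psychometric test administration and will liaise regularly with the clinical team".

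Section 2.3 also sets the clinical staffing: "Two therapists will be involved in the trial: one CBT-trained, the other trained in both CBT-F and MIT". It gives each arm its own supervisor.

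**The concern.** In a trial with many therapists in each arm, learning who treats a patient may say little about allocation. Here it says almost everything. The person who collects all the data is in regular contact with the clinicians and meets patients during treatment to collect a questionnaire about their therapy. The plan nevertheless relies on that person, or on someone it does not identify, being blind.

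At stake is a safeguard that the trial would report and might not have. An interviewer who knows the arm can rate an interview differently. Someone who hands out questionnaires can explain or prompt differently. A reader told that the research team was blind may also credit the self-reported primary result with a protection that assessor blinding cannot give it.

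**Working it through.** No figure in the plan depends on this point, so there is no stated value to reproduce. The check sets the sections side by side and adds a few counts.

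**1. Does the therapist reveal the arm?** Section 2.3 lists two therapists and describes only one as trained in MIT. It also gives the CBT-E arm and the MIT/CBT-F arm different supervisors. One therapist per arm is not written in those words, but it follows from the training and supervision described. Therapist identity is therefore a near-proxy for allocation.

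**2. Can the assistant learn the therapist?** The plan leaves two routes open.
- Contact with clinicians (2.3). Its content is not described or limited. Any exchange that links a patient to a therapist would reveal the arm.
- The WAI (2.5). It asks about the tasks and goals of therapy and the bond with the therapist. It is given monthly, and 2.5 assigns all measures to the assistant. Limiting contact with clinicians to scheduling would not close this route.

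No section withholds therapist identity from the assistant, and none provides for recording unblinding.

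**3. Is the assistant the blind researcher of 2.7.2?** The documents do not say.
- If they are the same person, 2.5 and 2.7.2 agree on who assesses, but the stated independence sits badly with regular contact with the clinicians.
- If they are different people, 2.5 and 2.7.2 disagree on who assesses.

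Either way the text needs to be reconciled.

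**4. How long does concealment last?** Section 2.6 ends it with an assessment stage that is not defined. Section 2.7 places screening and baseline measures before randomization. If the stage is baseline only, 2.6 promises no blinding of later assessments. If it runs through follow-up, the routes in step 2 bear on it directly.

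**5. Which measures are exposed?** Section 2.5 lists 11 instruments:

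| How 2.5 describes them | Instruments | Count |
|---|---|---|
| Labelled self-report | EDE-Q6, EAT-26, CIA, BES, STAI, BDI, DERS | 7 |
| Not labelled | SCL-90, TAS-20, WAI-SR | 3 |
| Interview | SCID-5 | 1 |

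Total: 7 + 3 + 1 = 11. Assessor knowledge bears most directly on the single interview. For the questionnaires it can act only through the way they are administered.

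**6. How many SCID-5 occasions?** Section 2.2 omits the SCID-5 only after session 10. That leaves the end of treatment plus 3, 6, 12, 18 and 24 months: 1 + 5 = 6 post-randomization occasions per patient. With 20 patients and no dropout the ceiling is 6 × 20 = 120 interviews. The sentence on SCID-5 timing in 2.5 is incomplete, so both counts depend on 2.2.

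**The case against.** The strongest reply is that nothing in the text shows the blind being broken. Contact with the clinical team could be purely about scheduling, and that team is not defined as the two therapists alone. Section 2.7.2 repeats that the assessor is blind. The sentence in 2.6 sits under randomization and may mean only that allocation is concealed until baseline assessment is complete, in which case later contact does not conflict with it. The named primary measure is self-reported, patients cannot practicably be blinded to which psychotherapy they receive, and this is a 20-patient pilot with a mainly descriptive analysis. Section 2.2 does not place the SCID-5 in any outcome tier.

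Much of this stands. A reader might infer that the stated blinding fails outright, or that contact with the clinicians unblinds the assistant with certainty. The documents do not support that: no section says that allocation or therapist identity is passed to the assistant. A reader might also infer a flat contradiction between 2.5 and 2.7.2, but that would require two different people, which is not stated. Differential prompting during questionnaires is a possibility, not something the documents show.

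What the reply does not remove is the absence of any safeguard. If contact is limited to scheduling, the plan should say so. If concealment ends at baseline, the plan should not leave readers to assume blinded follow-up. The WAI route remains on either reading of the contact with clinicians.

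**Conclusion.** The concern holds in this form: blinding is asserted in 2.6 and 2.7.2, is not protected by the arrangements in 2.3 and 2.5, and is at clear risk. It rests on two inferences: that each therapist treats one arm, and that the assistant's contact with clinicians is not restricted in some way the plan leaves out.

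The effect is moderate. It falls mainly on one of 11 instruments, the SCID-5, at up to six post-randomization occasions per patient if 2.2 governs the schedule, and secondarily on questionnaire administration. It has limited bearing on the EDE-Q6, which patients who know their therapy rate themselves. No sample size or analysis changes. What changes is what the trial may claim about protection from bias, and that should be corrected because doing so costs almost nothing.

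**What to change.** - **Section 2.3:** limit the assistant's contact with the clinical team to scheduling by study number, with no therapist names and no case discussion.
- **Section 2.5:** have the WAI returned in a form that does not show the assistant who the therapist is, for example self-completed and sealed. Complete the sentence on SCID-5 timing so that it agrees with 2.2.
- **Sections 2.6 and 2.7.2:** define the research team and the assessment stage. State whether the assistant is the blind and independent researcher, and whether concealment covers follow-up. If they are different people, assign the post-baseline SCID-5 interviews to the blind one.
- **Section 2.6, blinding sentence:** replace it with a statement that patients and therapists are not blind, that the EDE-Q6 is self-reported, and that assessor blinding is claimed only for the SCID-5 and only if this separation is kept. Add that unblinding events will be recorded, since a patient may name the therapist during an interview.

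The cost is slightly less convenient coordination and a more modest blinding claim. If the assistant and the blind researcher prove to be the same person, the SCID-5 claim rests on the contact limits and the handling of the WAI alone. Separating the roles would then need one more person, a somewhat larger cost.

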## 2.7 Procedure

Treatment-seeking participants at the CTI Disturbi Alimentari e Obesità will first receive an assessment screening visit. Once evaluated for inclusion/exclusion criteria, they will be informed about the study. If they wish to participate, they will be required to give written informed consent.

Tab.1. Flow chart of the study design

The researcher will ensure that the person is fully informed of the randomization process and their chances of receiving additional MIT sessions. Once informed and written consent has been obtained, baseline measures about primary and secondary outcomes will be completed.

Participants will then be randomized into two experimental conditions: CBT-F+MIT (experimental treatment) and CBT-E (standard treatment). All participants in each experimental condition will first receive two initial standard sessions mainly focused on investigating the compliance to the treatment and on understanding the maintenance factors of the ED.

**2.7.1. Experimental Treatment:** Participants in the CBT-F+MIT condition will receive a total of 20 sessions over 20 weeks. Specifically, 2 sessions will be based on CBT-F as usual only. During these sessions participants will receive psychoeducational training on eating behaviors and an introduction to the protocol tools, namely the monitoring form, weight chart, transdiagnostic formulation and Eating Problem Check List (EPCL).

These elements will be used at the beginning of the remaining 18 sessions, in order to monitor the regulations of eating behaviors as well eliciting narrative episodes. These materials will form the basis for the MIT-part of the session, in which therapists will seek to form with the patient a shared understanding of the psychological reasons underlying their ED symptoms and their maladaptive interpersonal functioning. Once a shared understanding is reached, patients and therapist will work to develop healthier strategies for managing negative thoughts and feelings antecedent to disordered eating. They will also develop new strategies for engaging in social interactions that meet their

relational basic wishes, such as attachment, personal worth, autonomy and group belonging (Dimaggio et al., 2015; 2020).

With MIT therapy, patients will be guided in to understand that perfectionism and the need for control they experience through ED are coping strategies developed within interpersonal patterns of interaction with significant others, where low self-esteem and emotive dysregulation play a central role.

Overall, MIT aims to improve individuals' capacity to make sense of their own affect and cognitions and become aware of being driven by maladaptive, rigid and biased schemas about self and others. This enables the individual to form a richer understanding of the mind of the others and use this knowledge to react in more adaptive ways to social difficulties or evolutionary selected wishes (such as being cared of, finding a satisfying place in the social hierarchy, explore the environment and be autonomous). MIT also enables individuals to reflect on how these schemas may act as triggers for disordered eating behavior and develop more effective coping strategies in face of interpersonal stressors.

MIT sessions will be integrated within the CBT-F protocol (Fairburn; 2003) which will provide psycho-educational, nutritional re-education and management for ED. In particular, CBT aims to inform patients about the importance of self-control, the dangers of some restrictive behaviors such as self-induced vomiting. Moreover, CBT provides strategies to patients in order to monitor their usually dysfunctional behaviors and so increasing their awareness (i.e., food diary method) while reducing the availability of food and encourages activities that are incompatible with overeating. Patients will be trained in problem solving in order to change these feelings, as well as in increasing their self-awareness in order to recognize irrational thoughts about their body weight and shape. Additionally, they will be gradually exposed to foods that they had been avoiding [20].

**2.7.2 Standard Treatment:** participants in the CBT-E condition will receive a total of 20 CBT-E sessions over 20 weeks. This will include the standard CBT-E protocol outlined above, without the additional MIT elements.

CBT-E treatment will consist of four stages. In the first Stage, the treatment will be focused on achieving a shared understanding of the patient's eating disorder and the related maintenance factors. In this phase the patient will be helped to regulate and stabilize his eating habits and so to address his weight concerns. In the second stage, progress made is reviewed in detail. In the third stage, the sessions will be focused on the central processes that are maintaining the psychopathology of the patient's eating disorder. In particular, this involves in addressing concerns about weight and body shape, cognitive and caloric dietary restriction, events and emotions that affect nutrition. in phase three and four clinical perfection, low global self-esteem, intolerance of emotions and interpersonal difficulties are also addressed.

Towards the end of the third stage and during the fourth stage, procedures will be also implemented to minimize the risk of short- and long-term relapse.

Each experimental condition will include up to 10 participants. In both conditions participants will receive an assessment session by a researcher who is blind and independent. In both arms, review session will be scheduled 2 weeks after the end of therapy to evaluate progress and to address any remaining or emerging issues.

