### 2.2 Study design

A parallel-group randomized controlled trial design will be used in order to compare CBT-E (n = 10) condition to combined MIT/CBT-F (n = 10). Patients in both conditions will receive 20 weekly sessions of either CBT-E or MIT/CBT-F.

Primary outcomes will be represented by ED and comorbid symptoms as assessed with the Eating Disorder Examination Questionnaire (EDE-Q6) (Fairburn & Beglin, 1994), which are expected to be

reduced after treatment. Other measures of ED and comorbid symptoms will still be considered primary outcomes. Secondary outcomes are anxiety, depression and global psychological symptoms. Lastly, exploratory outcomes will be difficulties in the emotional sphere such as understanding, processing, regulating or describing emotions.

Predictors, mediators and outcome variables will be measured at baseline, after 10 sessions with the exclusion of SCID-5 Interview, at the end of the treatment, and in the following 3, 6, 12, 18 and 24 months after the treatment. Two psychotherapies for each arm will be randomly selected, audio recorded and later analysed in order to explore the therapy process.

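### Section 2.7 tells candidates they may receive additional MIT sessions, but both arms have 20 sessions; the wording is inconsistent with the design and could make CBT-E look like the lesser arm

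*Combined protocol and SAP*

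**What the plan says.** Section 2.7 (Procedure) describes what happens before written consent, baseline measures and randomization. The researcher is to make sure that the candidate is "fully informed of the randomization process and their chances of receiving additional MIT sessions".

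The sections that define the treatments describe the difference between the arms in another way:

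- Section 2.2: "Patients in both conditions will receive 20 weekly sessions of either CBT-E or MIT/CBT-F".
- Section 2.7.1, experimental arm: "Participants in the CBT-F+MIT condition will receive a total of 20 sessions over 20 weeks". Of these, "Specifically, 2 sessions will be based on CBT-F as usual only", and for the monitoring tools introduced there, "These elements will be used at the beginning of the remaining 18 sessions", each of which then has an MIT part.
- Later in 2.7.1: "MIT sessions will be integrated within the CBT-F protocol".
- Section 2.7.2, standard arm: "participants in the CBT-E condition will receive a total of 20 CBT-E sessions over 20 weeks", "without the additional MIT elements".

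Section 2.7 also gives both arms the same two introductory sessions, and the end of 2.7.2 gives both arms the same review session two weeks after therapy.

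**The concern.** A candidate told of a chance of additional sessions would reasonably conclude that one arm offers more therapy than the other. The treatment sections say otherwise. The sentence is a stated study procedure, so a team that follows the protocol literally would misdescribe what randomization decides.

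Three features of this trial make that matter:

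- **Masking.** Section 2.6 and the end of 2.7.2 describe blinding of the research team and of the assessing researcher. No section masks participants, and in a comparison of two talking therapies they will usually know what they receive.
- **Outcomes.** Section 2.2 makes the EDE-Q6 primary, together with other measures of eating disorder and comorbid symptoms. Section 2.5 describes the EDE-Q6, EAT-26, CIA and BES as self-report. A blinded assessor does not protect a score that the participant supplies.
- **Retention.** Section 2.4 reports dropout by arm, and section 4 judges tolerability by attendance and dropout.

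A participant who believes that CBT-E means missing something extra could rate symptoms less favourably or leave earlier. Both would favour MIT/CBT-F. Baseline measures are taken before allocation, so adjusting for them would not remove a reaction to the allocation. Section 2.5 lists no expectancy or credibility rating with which to look for one.

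**Working it through.** **Session count**

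| Component | MIT/CBT-F | CBT-E | Source |
|---|---|---|---|
| CBT-F only | 2 | – | 2.7.1 |
| With an MIT part | 18 | – | 2.7.1 |
| CBT-E | – | 20 | 2.7.2 |
| Total | 2 + 18 = 20 | 20 | agrees with 2.2 |

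The plan's stated total of 20 for the experimental arm is reproduced. Additional sessions = 20 − 20 = 0.

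The two introductory sessions and the review session do not change this. The text does not settle whether the introductory sessions fall inside the 20. If they do, the comparison is 20 against 20. If they are extra, it is 22 against 22. Adding the review session gives 21 against 21 or 23 against 23. The difference is 0 in every case.

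**Can the word be read as added content?**

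Set the two arms against their common base. The Introduction describes CBT-E as CBT-F with an added focus on maintenance factors. Section 2.7.2 assigns work on perfectionism, self-esteem, intolerance of emotions and interpersonal difficulties to the later stages of CBT-E. The comparison is therefore:

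- experimental arm: CBT-F plus MIT, in 20 sessions;
- standard arm: CBT-F plus the enhanced modules, in 20 sessions.

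Relative to CBT-F, MIT is an addition. Relative to the comparator that candidates may actually be allocated, it is an alternative to the enhanced modules. Reading sessions as content brings the sentence closer to the design but still does not describe the choice correctly.

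**Size of the possible bias**

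The documents give no expectancy data, no standard deviation for any scale, no significance level and no target difference. The effect of the wording on self-ratings or dropout cannot be calculated from them.

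**The case against.** The strongest reply is that this is loose wording in a one-sentence summary of a consent discussion. Section 2.7.1 itself uses the term MIT sessions for work carried out inside CBT-F sessions, and section 2.7.2 speaks of elements. The same sentence in 2.7 requires full information about randomization. The patient sheet is not part of the text reviewed, so nothing shows that session counts are withheld or that CBT-E is described as inferior. All of this is fair. It limits the claim to what the protocol instructs and what that could cause. The instruction itself still disagrees with the treatment sections.

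A second reply is that everyone hears the same information before randomization, so any difference between arms arises only once participants know their allocation. That happens in any open comparison of an experimental with a standard therapy. This also stands: neutral wording removes one avoidable contribution and leaves the rest.

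Several stronger readings are tempting, but the documents do not support them:

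- **That the wording does bias the results.** No expectancy information is given. The plan supports *could*, with a plausible direction and unknown size.
- **That it inflates the false-positive rate by a definite amount.** Any figure would need an invented shift in scores and a test at a level the plan does not state. Section 3 is mainly descriptive, with exploratory models.
- **That every primary outcome is self-report.** Section 2.2 does not list the further primary measures, and section 2.5 includes the SCID-5 interview. The statement is secure only for the four scales named above.
- **That it undermines the dropout benchmark.** Section 4 sets the expected dropout of under 10–15% in the MIT arm against a literature average of 17.51%, not against the CBT-E arm. Only the by-arm comparison is exposed.
- **That section 2.7.2 is also wrong.** It is accurate that CBT-E lacks the MIT elements, and that sentence is not described as told to patients.

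**Conclusion.** The point holds as an inconsistency with a plausible consequence. Section 2.7 has candidates informed about additional sessions, and the plan provides none: 20 against 20. The arms differ in the content of 18 of the 20 experimental sessions, and the comparator is an active treatment of equal length.

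The possible consequence is expectancy or disappointment bias in favour of MIT/CBT-F, in the self-rated eating disorder scales and in dropout by arm. This rests on two inferences: that participants will know their treatment, because no section masks them, and that what they are told resembles the protocol sentence. No numerical size can be attached.

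In a pilot of 10 per arm with mainly descriptive analyses, importance is minor to moderate. The issue affects how between-arm differences in self-report and retention are read, not a confirmatory test.

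**What to change.** In section 2.7, replace the phrase about additional MIT sessions with neutral wording. For example: participants have an equal chance of one of two active treatments, each of 20 weekly sessions and differing in content, and it is not known which is better. Check that the patient information sheet and the researcher's spoken explanation say the same. Section 2.7.2 needs no change.

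The cost is a wording change in the protocol and, if the sheet carries the same phrase, in the patient information, with a minor notification to the ethics committee. Treatment, sample size and analysis are unaffected. The change should be made before recruitment, or for the participants still to be approached, because later analysis cannot undo expectations already formed.

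The change will not remove the bias that comes from participants knowing their arm. A brief baseline rating of treatment expectancy or credibility would be a useful optional addition, because it would let the report describe that remaining issue.
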